### 16. Safety reporting

All adverse events (AE) related to or thought to be related to the procedure will be recorded in the patient's eCRF using an adverse event form. This form will record the nature, severity, time of onset of, and treatment required for the AE. Severity of the AE is graded according to the Clavien-Dindo classification (see Section 5.4)

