#### 6.4 Secondary endpoint

#### 6.4.1 Safety

Expected adverse event (AE) related to BTXA injection of the puborectalis include:

- Bruising at injection site
- Local skin reaction at injection site
- Pain at injection site
- Infection at injection site
- New or worsening faecal incontinence

Following the injection, any adverse event reported by the patients will be recorded on the adverse event (AE) form on the patient's eCRF using Research Electronic Data Capture (REDCap). This form will record the nature, severity, time of onset of, and treatment required for the AE. Patients are encouraged to self-report any adverse events as soon as possible by telephone. If no adverse events have been self-reported this will be confirmed with the patient at the end of every follow-up appointment as part of the follow-up procedure. In addition, at the time of first follow-up the injection site will be inspected for any signs of bruising, local skin reaction, or infection. At each follow-up, St. Mark's incontinence score will also be measured to allow detection of new or worsening incontinence, which is the main procedure specific risk associated with this procedure.

The severity of any adverse events will be classified according to the Clavien-Dindo classification of surgical complications:

- Grade 1 any deviation from normal post-operative course without need for pharmacological (antiemetics, antipyretics, analgesics, diuretics, and electrolytes are permitted), surgical, endoscopy, or radiological interventions
- Grade 2 requiring pharmacological treatment other than those permitted in 1 (including blood transfusion and total parenteral nutrition)
- Grade 3 requiring surgical, endoscopic, or radiological intervention
  - Grade 3a not under general anaesthetic
  - Grade 3b under general anaesthetic
- Grade 4 life-threatening complication requiring intensive care management
  - Grade 4a single organ dysfunction, including dialysis
  - Grade 4b multi-organ dysfunction
- Grade 5 death

Serious adverse events (SAE) will be recorded as above and will also be reported as described in the safety reporting section (see Section 16).

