### 8. Study design

The overall design is of a single-centre, prospective, uncontrolled, open-label observational study. Patients diagnosed with dyssynergic defaecation, using Rome IV criteria, will be identified from weekly pelvic floor MDT and current waiting list for biofeedback therapy and invited to participate. BTXA injection is not offered as an alternative to biofeedback and does not preclude patients from receiving biofeedback therapy as per standard treatment as this is not a study of treatment efficacy.

All participants will undergo BTXA injection within 12 weeks of recruitment.

Data collection:

- Baseline data collection from patient's initial symptoms questionnaire and anorectal physiology report (pre-procedure).
- MYMOP questionnaire (pre-procedure and at final follow-up)
- Patient and physician procedural questionnaire to be completed at the end of the BTXA injection procedure (see Section 5.3 and 5.4).
- Cleveland clinic constipation score and St. Mark's incontinence score to be completed by the patient at each follow-up.
- Anorectal physiology report (post-procedure) for anorectal manometry results at first follow-up.
- Any adverse events reported by the patient will be recorded on an adverse event form (see Section 5.4).

Data analysis:

- Feasibility and efficacy outcomes will be extracted from the questionnaires and reports and recorded onto Research Electronic Data Capture (REDCap).
- Anonymised summary data will be exported to Excel and descriptive statistics (e.g. mean, confidence intervals of effect) used to present data for publication.

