At any stage of the study, expected adverse events will be recorded on the patient's eCRF. If no adverse events have been self-reported this will be confirmed with the patient at the end of every follow-up appointment as part of the follow-up procedure. Serious or unexpected adverse events will be recorded and also reported according to research governance framework guidelines (see Section 14).

Patients can withdraw at any point in the study without the requirement to provide a reason. The data collected from the point of consent to the point of withdrawal will be kept for analysis of retention and follow-up rate, as well as incidents of adverse events depending on the stage at withdrawal. Such patients will return to routine care.

					-~~{	Lon				

Figure 3a. EMG of puborectalis demonstrating tonic activity at rest

Figure 3b. EMG of puborectalis demonstrating voluntary contraction

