#### 16.1Adverse Events (AEs)

An AE is any untoward medical occurrence in a participant to whom an intervention has been administered, including occurrences which are not necessarily caused by or related to that intervention. An AE can therefore be any unfavourable or unintended sign (including an abnormal laboratory finding), symptom or disease temporally associated with study activities.

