#### 16.2Adverse Reaction (ARs)

An AR is any untoward and unintended response in a participant to an intervention. All adverse events judged by either the reporting investigator or the sponsor as having a reasonable causal relationship to the intervention qualify as adverse reactions. The expression 'reasonable causal relationship' means in general that there is evidence or an argument to suggest a causal relationship.

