#### 16.3Notification and reporting of Adverse Events and Reactions

If the AE is not defined as serious, the AE will be recorded in the study documents and the participant followed up by the research team. The AE will be documented in the participants' source documents, the Case Report Form (CRF), and, where appropriate, medical records.

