#### 16.8Overview of the Safety Reporting responsibilities

The CI is the medical assessor on behalf on the sponsor and will review all events reported. The CI will ensure that safety monitoring and reporting is conducted in accordance with the sponsor's requirements.

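### The Section 16 lead-in limits the adverse event form to events thought related to the procedure, contradicting Sections 6.4.1, 8 and 16.3, which set no such condition

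*Combined protocol and SAP*

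**What the plan says.** The protocol gives a recording rule for adverse events in five places.

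- Section 16, lead-in: "All adverse events (AE) related to or thought to be related to the procedure will be recorded", on an adverse event form in the eCRF.
- Section 6.4.1: after the injection, "any adverse event reported by the patients will be recorded on the adverse event (AE) form", on the same eCRF. No relatedness condition.
- Section 8: "Any adverse events reported by the patient will be recorded on an adverse event form". No relatedness condition.
- Section 16.3: "If the AE is not defined as serious, the AE will be recorded in the study documents", and also in source documents, the CRF and, where appropriate, medical records. No relatedness condition.
- Section 9, after the description of the intervention: "At any stage of the study, expected adverse events will be recorded on" the eCRF, while serious or unexpected events are recorded and also reported. This rule is worded by expectedness, not relatedness.

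Three further sections bear on the point. Section 16.1 defines an adverse event as "including occurrences which are not necessarily caused by or related to that intervention". Section 16.2 classes an event as an adverse reaction when it is "judged by either the reporting investigator or the sponsor as having a reasonable causal relationship" to the intervention. Section 16.8 makes the chief investigator the medical assessor, who "will review all events reported".

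**The concern.** In the protocol's own scheme an event first counts as an adverse event, and relatedness is judged afterwards to decide whether it is a reaction. The Section 16 lead-in applies that test at entry to the form. An event that staff attribute to another cause then need not be entered, although three other rules require it.

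Safety is the first-listed secondary objective, and the study is uncontrolled and open-label with 10 patients. With no comparison group, attribution of a single event is uncertain, and a pattern across patients can be seen only if the events were recorded first. If the narrow rule is followed, the adverse event summary is understated.

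**Working it through.** The plan states no figure on this point, and Section 11.1 gives the sample size as a convenience sample, so there is nothing to reproduce. The check is a comparison of the rules.

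**Step 1: one event under each rule.** Take a hypothetical non-serious event: a patient telephones three weeks after the injection with urinary symptoms that staff put down to another cause.

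| Place | Condition for recording | Result |
|---|---|---|
| 6.4.1 | reported by the patient after injection | on the form |
| 8 | reported by the patient | on the form |
| 16.3 | not serious | study documents, source documents, CRF |
| 9 | expected: eCRF; serious or unexpected: recorded and reported | recorded, by a route that depends on expectedness |
| 16 lead-in | related or thought related to the procedure | not required on the form |

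The lead-in alone does not require entry. Section 16.1 is a definition and not a recording rule; its role is to confirm that the event is an adverse event.

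**Step 2: what would recover an event left off the form.** Sections 6.4.1 and 16 list the form's contents as nature, severity, time of onset and treatment. Relatedness is not among them, so the Section 16.2 judgement has no listed place on the form. No section describes a log of events judged unrelated, or says who judges relatedness at entry. The chief investigator's review covers reported events. Section 17 does not require on-site monitoring, although Section 14.1 says that eCRFs can be verified against the original records.

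**Step 3: which events are exposed.** Section 6.4.1 uses the St. Mark's incontinence score at each follow-up to detect new or worsening incontinence, and has the injection site inspected at the first follow-up. Those harms have a separate check. Section 15.3 also lists common drug effects away from the site, such as urinary disorders, muscle weakness and falls. No scheduled study instrument is assigned to these, so they depend on the adverse event form.

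**Step 4: scale at n = 10 (illustration only).** Suppose one patient has such an event and it is not entered. The proportion moves from 1/10 = 10% to 0/10 = 0%. Exact (Clopper-Pearson) 95% limits:

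- 1/10, lower: 1 − 0.975^(1/10) = 0.0025, or 0.3%.
- 1/10, upper: the p solving (1 − p)^10 + 10p(1 − p)^9 = 0.025, which is 0.445, or 44.5%.
- 0/10, lower: 0%. Upper: 1 − 0.025^(1/10) = 0.308, or 30.8%.

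**The case against.** The strongest reply is that Section 16.3 sits inside Section 16 and still requires every non-serious event in the source documents and the CRF. Sections 6.4.1 and 8 require it too, and Sections 6.4.1 and 9 have adverse events checked with the patient at the end of every follow-up. Loss needs staff to follow one lead-in sentence over three explicit rules. That sentence does not contain the word only, and it does not forbid recording other events. This is correct, and it makes the loss conditional.

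Four stronger readings are tempting, and the documents do not support them.

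- **That filtered events are gone for good.** Section 16.3 keeps non-serious events in source documents, so permanent loss is not established.
- **That events are dropped before the medical assessor sees them.** The entry-stage judge is not named and could be the chief investigator. Bypassing the assessor is left open; it is not a stated step.
- **That the lead-in's reference to the procedure shuts out drug effects.** Section 9 uses intervention and procedure for the same injection of BTXA, Section 5.3.1 speaks of procedure-specific side-effects of BTXA injection, and Section 6.4.1 treats incontinence as one of these. In this protocol the term includes drug effects.
- **That incontinence would be undercounted.** The cited transanal rates give 0.069 × 10 = 0.69 expected cases of faecal incontinence and 0.041 × 10 = 0.41 of flatus incontinence. But Section 15.3 lists both as procedure specific, so they fall inside the lead-in's wording. Faecal incontinence is also an expected event under Section 6.4.1, and the St. Mark's score checks for incontinence independently. These counts say nothing about the events at risk.

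It is also fair that Section 11.2 names only a qualitative summary for reported adverse events, so the 10-point shift is not a planned statistic. What survives is the contradiction itself: the rules cannot all govern the same form, and the narrower one opens the safety section.

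**Conclusion.** The recording rule is wrong as written, because it contradicts itself. The Section 16 lead-in conflicts directly with Sections 6.4.1, 8 and 16.3, and it is out of order with Sections 16.1 and 16.2. The likely effect is limited: some non-local events attributed to other causes may be left off the form, which would understate adverse events in the safety summary. This assumes that some staff apply the lead-in rather than the other rules, and that such events occur. The documents give no rate for either, so no expected number of missed events can be calculated. At 10 patients, a single omission is enough to turn one affected patient into none. No sample size or planned efficacy analysis is affected.

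**What to change.** - In the Section 16 lead-in, delete the clause that restricts recording to events related, or thought related, to the procedure.
- Use one rule in Sections 6.4.1, 8, 9, 16 and 16.3: every adverse event is entered on the adverse event form, whatever its relatedness or expectedness. Expectedness then decides only onward reporting.
- State a single recording period. Section 6.4.1 starts after the injection, whereas Section 9 speaks of any stage of the study; these need to be reconciled.
- Add a field to the form for relatedness to BTXA or to the procedure. It is completed after entry by the assessors that Section 16.2 names (the reporting investigator or the sponsor) and reviewed by the chief investigator under Section 16.8.

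The cost is a short wording amendment, one form field, and a few extra entries for unrelated minor events in 10 patients.

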#### 16.1Adverse Events (AEs)

An AE is any untoward medical occurrence in a participant to whom an intervention has been administered, including occurrences which are not necessarily caused by or related to that intervention. An AE can therefore be any unfavourable or unintended sign (including an abnormal laboratory finding), symptom or disease temporally associated with study activities.

#### 16.2Adverse Reaction (ARs)

An AR is any untoward and unintended response in a participant to an intervention. All adverse events judged by either the reporting investigator or the sponsor as having a reasonable causal relationship to the intervention qualify as adverse reactions. The expression 'reasonable causal relationship' means in general that there is evidence or an argument to suggest a causal relationship.

#### 16.3Notification and reporting of Adverse Events and Reactions

If the AE is not defined as serious, the AE will be recorded in the study documents and the participant followed up by the research team. The AE will be documented in the participants' source documents, the Case Report Form (CRF), and, where appropriate, medical records.

#### 16.4Serious Adverse Events (SAEs) or reactions

A serious adverse event (SAE) is defined as an untoward occurrence that:

- Results in death,
- Is life-threatening,
- Requires hospitalisation or prolongation of existing hospitalisation,
- Results in persistent or significant disability or incapacity,

- Consists of a congenital anomaly or birth defect, or
- Is otherwise considered medically significant by the investigator.

SARs will be reported to the REC where in the opinion of the CI the event was serious and:

- Related (it may have resulted from administration of any of the research interventions), and
- Unexpected (the type of event is not listed in the protocol or other Reference Safety Information as an expected occurrence).

#### 16.5Notification and reporting of Serious Adverse Events

Serious Adverse Events (SAEs) that are considered to be 'related' and 'unexpected' will be reported to the sponsor within 24 hours of learning of the event, and to the REC within 15 days in line with the required timeframe.

#### **16.6Urgent Safety Measures**

The CI will take urgent safety measures if necessary to ensure the safety and protection of the clinical study participant from immediate hazards to their health and safety. The measures will be taken immediately. The approval of the REC prior to implementing urgent safety measures is not required. However, the CI will inform the sponsor and REC (via telephone) of this event immediately.

The CI will inform the REC in writing within 3 days, in the form of a substantial amendment. The sponsor (Joint Research Management Office (JRMO)) will be sent a copy of the correspondence with regards to this matter.

#### **16.7Annual Safety Reporting**

The CI will send the Annual Progress Report to the REC using the HRA template (the anniversary date is the date on the REC "favourable opinion" letter) and to the sponsor.

#### 16.8Overview of the Safety Reporting responsibilities

The CI is the medical assessor on behalf on the sponsor and will review all events reported. The CI will ensure that safety monitoring and reporting is conducted in accordance with the sponsor's requirements.

### 17. Monitoring and auditing

The sponsor or delegate retains the right to audit any study, study site, or central facility. Any part of the study may be audited by the funders, where applicable.

On-site monitoring is not required given the small study size and being conducted on a single site.

### 19. Finance and funding

This study will utilise departmental funding as the procedure is a part of standard clinical care. Additional equipment specific to this technique (EMG needle), patient travel expenses, and cost of research staff is provided by Bowel Research UK small grant for the 12-months period of the study.

# 20. Indemnity

The insurance that Queen Mary University of London has in place provides cover for the design and management of the study as well as "No Fault Compensation" for participants, which provides an indemnity to participants for negligent and nonnegligent harm.

### 21. Dissemination of research findings

Findings will be subjected to oral presentation in a specialist research meeting, reporting in an appropriate peer reviewed journal, and will also be disseminated through the Bowel Research UK website. It will also form part of the research fellow's PhD thesis.

